- d: CT scan of the abdomen, pelvis and chest or hepatic MRI and CT scan of the pelvis and chest without injection; RECIST criteria version 1.1
- e: Paraffin-embedded human solid tissue blocks will be sent off at room temperature at the end of the inclusions
- 1: A 12-lead ECG will be performed at the end of every other cycle (8 weeks, if there's no postponed treatment)
- 2: D1 and D15 of the first two cycles for Bras B (Stivarga®) and D1 only at the other cycles
- 3: Tumor markers CEA and CA 19-9 at every cycle
- 4: If the last clinical and laboratory evaluations > 7 days
- 5: if not done at the EOT visit
- 6: If the last radiological tumor assessment > 1 month
- 7: C1-C2 D8 (arm A): vital signs without height, weight and BSA
- 8: As applicable
- 9: A treatment diary will be handed over to patient on cycle 1 day 1
- 10: EORTC QLQ-C30 questionnaires will be completed by the patient on Day 1 of Cycle 1 then at each evaluation (= 8 weeks) for both treatments

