5.3 Treatment period

REGIRI or Regorafenib:

After all screening assessments have been completed and the patient's eligibility has been confirmed and documented, the patient will be randomized.

The following assessments should be performed on the first day and day 15 of each cycle (REGIRI) or cycle (Regorafenib) except C1D1 prior to receiving study treatment (+/- 3 days):

- Physical examination with weight, body surface area (if the patient's body weight changes by more than 10 % then BSA will be recalculated for Regorafenib and it will be recalculated for any change of weight for Irinotecan) and vital signs (heart rate, blood pressure)
- ECOG performance status :
- Adverse events documentation (including Start/Stop dates, seriousness, CTC notation and grading, relationship to study drug, outcome and action taken) using CTCAE V5.0
- Concomitant medications (including start/stop dates, dose, indication)
- 12-lead ECG. It will be performed every other cycle (8 weeks if there's no postponed treatment) for both arms
- The following laboratory evaluations are not required at Day 1 of Cycle 1 if these
 were completed within 7 days of starting study drug treatment. Otherwise, these
 laboratory evaluations are required on Day 1 and 15 of each cycle:
 - → CBC with differential should be performed: RBC, hemoglobin, hematocrit, platelet count and WBC. WBC must include differential neutrophil, lymphocyte, monocyte, basophil and eosinophil counts
 - → Coagulation panel: Prothrombin time (PT) or the International Ratio of PT (PT-INR) and Partial Thromboplastin Time (PTT)
 - → Electrolyte panel: sodium, potassium, chloride, calcium
 - → Chemistry panel : albumin, lipase, phosphate, glucose, serum creatinine, clearance calculated according CKD-EPI (appendix 7)
 - → Hepatic panel: Aspartate Amino-Transferase (AST), Alanine Amino-Transferase (ALT), bilirubin (total and direct), GGT, alkaline phosphatase, Lactic Dehydrogenase (LDH)

- → Thyroid function test (TSH, free T3, free T4, on day 1 of each cycle for both arms)
- Tumor markers CEA (Carcino-Embryogenic Antigen), CA 19-9 (carbohydrate Antigen 19-9) every cycle for both treatments
- A β-HCG dosage for women of childbearing potential. Post-menopausal women with no menses for at least 1 year or surgically sterilized women will not be required to undergo a pregnancy test (on day 1 of each cycle for both arms).
- Urine analysis by urinary dipstick. If results of protein ≥ 3+, then quantification

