 of proteinuria on a 24-hour urine collection must be done.
- EORTC QLQ-C30 (appendix 2) questionnaires will be completed by the patient on Day 1 of Cycle 1 (baseline) then on the first day of every other cycle (every 8 weeks)
- Drug dispensing
- Drug accountability (pharmacy). To have complete control over the distribution and use of the study drug, the drug accountability must be performed on Day 1 for arm A (REGIRI) and B (Regorafenib) of each cycle

Provide patient's diary on C1D1. It will allow to patient to write down his oral intakes and blood pressure values

The blood pressure must be monitored weekly for the first six weeks of study treatment. The blood pressure will be recorded by the patient and entered onto his treatment diary. In the latter case, the patient should be instructed to contact the physician in the event of systolic \geq 150 mm Hg and / or diastolic \geq 100 mm Hg. The physician should confirm the reading before recording it into the e-CRF. Blood pressure measurements will be performed in patients sitting for 5 minutes prior to the evaluation. The patient should be instructed to take their blood pressure in the morning and repeat two more times for accuracy.

The following assessments should be performed on day 8 of cycle 1 and 2:

REGIRI (arm A)

- Vital signs (Heart rate and blood pressure)
- these laboratory evaluations are required: Aspartate Amino-Transferase (AST), Alanine Amino-Transferase (ALT), bilirubin (total and direct)

Stivarga® (Regorafenib) (arm B):

• Phone call by a treatment nurse for knowing if there are any adverse events and blood pressure value (current state of the art)

The following assessments should be performed on day 15 of cycle 1 and 2:

REGIRI (arm A)

- Physical examination with weight and vital signs (heart rate, blood pressure)
- ECOG performance status
- Concomitant medications (including start/stop dates, dose, indication)
- Adverse events documentation (including Start/Stop dates, seriousness, CTC notation and grading, relationship to study drug, outcome and action taken) using CTCAE V5.0
- A CBC with differential should be performed: RBC, hemoglobin, hematocrit, platelet count and WBC. WBC must include differential neutrophil, lymphocyte, monocyte, basophil and eosinophil counts
- Coagulation panel: Prothrombin time (PT) or the International Ratio of PT (PT-INR) and Partial Thromboplastin Time (PTT)
- Electrolyte panel: sodium, potassium, chloride, calcium

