- Chemistry panel: albumin, lipase, phosphate, glucose, serum creatinine, clearance calculated according CKD-EPI (appendix 7)
- Hepatic panel: Aspartate Amino-Transferase (AST), Alanine Amino-Transferase (ALT), bilirubin (total and direct), GGT, alkaline phosphatase, Lactic Dehydrogenase (LDH)
- Urine analysis by urinary dipstick. If results of protein ≥ 3+, then quantification of proteinuria on a 24-hour urine collection must be done.
- Drug accountability (pharmacy)
 Verify patient's diary. It will allow to patient to write down his oral intakes and blood pressure values

The following assessments should be performed on day 15 of cycle 1 and 2:

Stivarga® (Regorafenib - arm B):

• these laboratory evaluations are required: Aspartate Amino-Transferase (AST), Alanine Amino-Transferase (ALT), bilirubin (total and direct)

The following assessments should be performed on day 22 of cycle 1 and 2:

REGIRI (arm A):

- Phone call by a treatment nurse for knowing if there are any adverse events and blood pressure value (current state of the art)
- These laboratory evaluations are required: Aspartate Amino-Transferase (AST),
 Alanine Amino-Transferase (ALT), bilirubin (total and direct)

The following assessments should be performed at each evaluation i.e (every 8 weeks):

REGIRI or Regorafenib:

 Tumor markers CEA (Carcino-Embryogenic Antigen), CA 19.9 (Carbohydrate Antigen 19-9)

 Radiological tumor assessment using the RECIST criteria, version 1.1 (see Appendix 5) must be performed. (CT scan of the abdomen, pelvis and chest or hepatic MRI and CT scan of the pelvis and chest without injection)

A PET scan is not acceptable for radiological evaluation. Throughout the study, the identical lesions to those identified and measured at baseline must be evaluated using the same technique, and preferably by the same radiologist. Copies of all CT scans performed for tumor assessment in non-progressive enrolled patients will be stored on CDs at the site

 EORTC QLQ-C30 (appendix 2) questionnaires will be completed by the patient at each evaluation i.e 8 weeks

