6.1 Experimental treatment or procedures

Experimental arm: REGIRI (arm A)

[figure not shown]

Figure 1: REGIRI regimen

The treatment schedule will be as follows:

- Starting on days 1 and 15 of each 28-day cycle, all patients will receive irinotecan as an intravenous infusion over a 90 minute period.

The initial dose of irinotecan will be 120 mg/m².

The dose for the second infusion of irinotecan will be 150 mg/m² over 90 minutes if no diarrhea of grade >1 NCI-CTCAE V 5.0 grading or others toxicities of grade >2 occur.

The dose for the third and subsequent infusions of irinotecan will be 180 mg/m² over 90 minutes under the same conditions as for the 2nd infusion.

- -On days 2–8 and 16–22 of each cycle, all patients will receive Regorafenib 160 mg orally once daily.
- -A chemotherapy course = 15 days, 1 cycle = 4 weeks

Control arm: Stivarga® (Regorafenib) (arm B)

-Regorafenib will be given orally at a dose of 160 mg once daily over 3 weeks then one week off.

1 cycle = 4 weeks

[figure not shown]

Figure 2: Regorafenib schedule

The following products will be used in the study:

- Regorafenib, 40 mg tablets
- Irinotecan, 180 mg/m² IV (20 mg/ml)

ARM A: REGIRI (Regorafenib + Irinotecan)

Irinotecan

See manufacturer's product information (Appendix 8).

Irinotecan will be prescribed by each center and used in its marketed form.

The irinotecan will be diluted in a 5 % glucose solution or a 0.9% sodium chloride solution. The irinotecan will be delivered over 90 minutes as an intravenous infusion.

Regorafenib

For Packaging, List of excipients and Storage: See Investigator's brochure (Appendix 8).

Regorafenib® will be provided by Sponsor as tablets of 40 mg.

The investigational product(s) label will bear sponsor's name, address and telephone number, the EudraCT number, product name, dosage form and strength, quantity of investigational product par container, batch number, expiration date, dosing instructions, required storage conditions and required caution statements and/or regulatory statements as applicable.

Protocole NEXT-REGIRI -Version 6.0 du 09/11/2023

Page 39 sur 86

Receipt, distribution, return and destruction (if any) of the study drug must be properly documented.

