	occurence	permanently	
> 20 times ULN (Grade 4)	Any	Discontinue regorafenib	
	occurence	permanently	
> 3 times ULN (Grade 2 or higher) with	Any	Discontinue regorafenib	
concomitant elevation of bilirubin > 2 times	occurence	permanently	
ULN		Control liver function every	
		week until resolution or	
		return to baseline	

Termination of Regorafenib:

- -In the event of gastrointestinal perforation or fistula develops
- -In the event of reversible Posterior Encephalopathy Syndrome (REPS)
- -In the event of the appearance of cardiac ischemia and/or infarction

Other toxicities

The other toxicities will have to manage symptomatically, if possible. For any toxicity grade \geq 2 at D15 except alopecia and anemia, the irinotecan will be delayed up to two weeks and the toxicity will have to be grade \leq 1 to perform the course.

ARM B: STIVARGA® (REGORAFENIB)

Dosage changes should be made in 40 mg increments (1 tablet). The recommended daily dose of Regorafenib is 160 mg.

Dose reductions of Stivarga ®
1st reduction: 120 mg
2 nd reduction: 80 mg

Table b

Table 10: Dose modification/Delay for toxicities related to study drug (except handfoot Skin reaction and hypertension)^a

NCI-CTC V5.0	Dose	Dose Modification	Dose for Subsequent Cycles
	Interruption		
Grade 0-2	Treat on time	No change	No change
Grade 3	Delay until <	Reduce 1 dose level ^c	If toxicity remains < Grade 2,

Protocole NEXT-REGIRI -Version 6.0 du 09/11/2023

Page 52 sur 86

	Grade 2 ^b		dose re-escalation can be
			considered at the discretion
			of the treating investigator.
			If dose is re-escalated and
			toxicity (Grade 3) recurs,
			institute permanent dose
			reduction.
Grade 4	Delay until <	Reduce by 1 dose level ^c .	
	Grade 2 ^b	Permanent discontinuation	
		can be considered at	
		treating investigator's	
		discretion.	

a Excludes alopecia, non-refractory nausea/vomiting, non-refractory hypersensitivity and asymptomatic laboratory abnormalities.

Table 11: Dose modifications for hand-foot skin reaction

Skin Toxicity Grade	Occurrence	Suggested Dose Modification
Grade 1: Numbness,	Any	Maintain dose level and institute immediately
dysesthesia, paraesthesia,		supportive measures for symptomatic relief
tingling, painless swelling,		
erythema or discomfort of		
the hands or feet which		
does not		
disrupt the patient's normal		
activities		
Grade 2: Painful erythema	1st	Decreasing dose by one dose level and institute
and	occurrence	immediately supportive measures.

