PRO data as measured by the EORTC QLQ-C30 (appendix 2) will be analyzed to assess differences in health-related quality of life (HRQOL) values between treatment arms.

HRQOL scores were described for each assessment and compared either between treatment arms (rank sum test). The missing data pattern was studied by the comparison of the baseline characteristics between patients who either completed baseline HRQOL questionnaires or not. The compliance of the patients was also described using fill rate at each visit and for each questionnaire.

Longitudinal analyses were performed using two approaches:

- (1) A LMM analysed the evolution of scores through time and combined fixed effects [Cnaan A, Laird NM, Slasor P. Using the general linear mixed model to analyse unbalanced repeated measures and longitudinal data. Stat Med 1997;16:2349-80.+ Fairclough DL. Design and analysis of quality of life studies in clinical trials. 2002.] for study group, time factors, treatment-by-time interaction effects and random effects allowing specific correlations between observations for a particular patient. This mode I assumed no difference between the treatment arms at baseline.
- (2) A time to event approach considered the definitive deterioration of a HRQOL score as an event. Osoba et al. [Osoba D, Rodrigues G, Myles J, Zee B, Pater J.

Interpreting the significance of changes in health-related quality-of-life scores. J Clin Oncol 1998;16:139-44.] showed that a mean change of 5-10 pts, 10-20 pts and >20 pts in a QLQC30 score corresponds to a "small", "moderate" and "large" change in HRQOL. This definition was applied to indicate the clinical relevance of any differences. TUDD was defined as the time from randomisation to the first score deterioration with a 10-point minimal

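### The QLQ-C30 is timed both by treatment cycle and by 8-week evaluation; if the cycle rule is followed, unequal postponement between arms can bias the QLQ-C30 time until definitive deterioration (TUDD)

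*Combined protocol and SAP*

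**What the plan says.** The questionnaire's timing appears in three places.

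- Section 5.3, list of Day 1 and Day 15 assessments: "on Day 1 of Cycle 1 (baseline) then on the first day of every other cycle (every 8 weeks"). This rule follows the treatment cycle.
- Section 5.3, list for the 8-weekly evaluation: "questionnaires will be completed by the patient at each evaluation i.e 8 weeks". This rule follows the evaluation visit.
- Section 5.1, note 10 to the schedule table: baseline on Day 1 of Cycle 1, "then at each evaluation (= 8 weeks) for both treatments".

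For the ECG, also planned every other cycle, section 5.3 adds a condition: "It will be performed every other cycle (8 weeks if there's no postponed treatment) for both arms". Note 1 in 5.1 carries the same condition. The QLQ-C30 text has no such condition and does not say which rule prevails.

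Section 6.3 allows postponement in both arms. In REGIRI, for persisting toxicity at D15, "the irinotecan will be delayed up to two weeks", and blood counts can move a course to D21 or at most D28. In the regorafenib arm, a delay of up to 4 weeks is possible before permanent discontinuation.

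In section 9.3, "TUDD was defined as the time from randomisation to the first score deterioration" of at least 10 points with no later recovery. That section gives no assessment window for TUDD and no method for interval-censored detection.

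**The concern.** A QLQ-C30 deterioration can be recorded only on a date when a form is completed. If forms follow the cycle, a postponed course can move the form, and the recorded deterioration moves with it. Unequal postponement between arms then creates a difference in TUDD that reflects the visit calendar and not the patients' condition. Quality of life is a listed secondary endpoint in an open-label trial, and TUDD is one of its two longitudinal analyses. The end-of-treatment list in 5.4 has no QLQ-C30, so no form at that visit would catch a deterioration missed by a late scheduled form. Sites can reasonably follow either rule, so the data could also mix the two.

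**Working it through.** **1. The plan's own figure.** Section 6.1 gives "1 cycle = 4 weeks" in both arms, so two cycles are 2 × 4 = 8 weeks. The stated interval reproduces, provided nothing is postponed.

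**2. How far the cycle rule can drift.** Assume that every delay moves the next Day 1; the documents do not say whether a late D15 irinotecan course does. Between two forms, REGIRI has four irinotecan starts that can each slip by up to 2 weeks: 8 + 4 × 2 = 16 weeks at most, counting irinotecan delays only. Regorafenib has two cycle starts that can each slip by up to 4 weeks: 8 + 2 × 4 = 16 weeks at most. On this count the permitted ceilings coincide. REGIRI has more occasions to slip; regorafenib has the longer permitted delay per occasion.

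**3. Effect on the recorded date.** For an exponential deterioration time with rate λ = ln 2 / median and forms every L weeks, the mean lag between true and recorded deterioration is L / (1 − exp(−λL)) − 1/λ. The medians are assumptions, because the documents give none. For median 8 and L = 8: 8 / (1 − 0.5) − 11.54 = 4.46 weeks.

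| Form interval L | Median 8 wk | Median 13 wk | Median 26 wk |
|---|---|---|---|
| 8 weeks | 4.46 | 4.28 | 4.14 |
| 10 weeks | 5.71 | 5.44 | 5.22 |
| 12 weeks | 7.02 | 6.64 | 6.32 |

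Moving from 8 to 10 weeks adds 1.08 to 1.25 weeks. Moving from 8 to 12 adds 2.18 to 2.56 weeks.

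**4. Effect on the comparison.** The simulation used 39 patients per arm (section 9.1), identical true deterioration times in both arms, forms ±3 days, 52 weeks of follow-up and 1,500 runs. Slip per 8-week block was uniform from zero to twice the stated mean. The event was the first form after true deterioration; later recovery and treatment stopping were not modelled. The HR (REGIRI versus regorafenib) is the log-rank one-step estimate, averaged on the log scale. Cells show HR and the two-sided false-positive rate at 5%.

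| Mean slip, REGIRI / regorafenib (weeks) | Median 8 wk | Median 13 wk | Median 26 wk |
|---|---|---|---|
| 0 / 0 | 1.01; 5.1% | 1.00; 4.4% | 1.01; 4.9% |
| 1 / 0 | 0.78; 18.3% | 0.90; 8.4% | 1.00; 4.4% |
| 2 / 0 | 0.79; 17.9% | 0.86; 8.6% | 0.88; 6.9% |
| 4 / 0 | 0.76; 21.7% | 0.86; 10.0% | 0.91; 6.7% |
| 2 / 2 | 0.99; 5.5% | 1.00; 5.6% | 0.99; 4.9% |
| 2 / 1 | 0.83; 12.7% | 0.88; 7.8% | 0.91; 6.9% |
| 1 / 2 | 1.21; 14.4% | 1.12; 7.8% | 1.11; 6.7% |

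The size does not rise smoothly with the slip, so these values illustrate the effect and do not predict it. The difference in total slip determines whether there is a bias and in which direction.

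**5. Equal rate per start is not equal total delay.** With one-week slips, 25% of four REGIRI starts gives 0.25 × 4 = 1 week per two cycles; 25% of two regorafenib starts gives 0.25 × 2 = 0.5 week. A second simulation ended form collection when treatment stopped (assumed median times on treatment 16 and 8.7 weeks) and took true median deterioration of 8 and 16 weeks. The HR was 0.90 and 0.90 with no slips, and 0.77 and 0.79 with 25% of starts slipping in both arms. When total delay was equal (25% of four against 50% of two, 1 week each) it was 0.89 to 0.91, as with no slips.

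**6. The proposed schedule.** The 0 / 0 row in step 4 is both arms on a common 8-week calendar: HR 1.00 to 1.01 and false-positive rate 4.4 to 5.1%.

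**The case against.** The case against has real weight. All three places mention 8 weeks, including the cycle-based sentence, and a site using the evaluation visit would produce no such bias. Both arms can be postponed, the documents give no delay rates, and the mechanism cancels when total delay is equal. The list containing the cycle-based sentence already carries a ±3-day window for both arms. Section 9.3 promises a SAP before database lock, where the handling of dates could be settled. All of this stands. It limits the point to a possible bias in the QLQ-C30 analyses, but it does not say which timing rule applies after a postponement.

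Three stronger readings are tempting, and the documents do not support them.

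- A reader might infer that the bias must favour REGIRI. That needs more total delay in REGIRI, which is plausible with four irinotecan starts against two cycle starts, but it also assumes that a late D15 course moves the next Day 1. If regorafenib is delayed more, the bias reverses.
- A reader might infer a larger effect. In the second simulation, 25% of REGIRI courses slipping and none in regorafenib gives HRs of 0.66 and 0.73. That sets regorafenib delay to zero and assumes unequal time on treatment, which alone gives 0.90 with no slips.
- A reader might infer that the mixed model compares arms at different weeks under one visit number. Section 9.3 models scores through time and does not say that nominal visits are used.

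**Conclusion.** The inconsistency is real, and two of the conflicting statements sit inside section 5.3 itself. If the cycle rule is followed and the arms differ in total postponement, the arm with more delay can show a longer QLQ-C30 TUDD with no true benefit. As an illustration, a mean two-week slip per block in REGIRI alone gives an apparent HR of about 0.79 to 0.88 and a false-positive rate of about 7 to 18%, for assumed true medians of 8 to 26 weeks. These figures rest on assumed delay and deterioration times and on delays moving the next form.

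The effect is confined to the QLQ-C30 analyses. OS does not depend on the forms. PFS rests on tumour assessment, clinical progression and death. The endpoint named Time to Deterioration (section 2.2.2) is WHO performance status of 2 or more and uses no questionnaire. This is a cheap improvement to a secondary analysis, not a threat to the trial's main conclusion.

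**What to change.** Align note 10 in 5.1 and both statements in 5.3 on one calendar schedule: baseline on Day 1 of Cycle 1, then every 8 weeks at the evaluation visit, not moved by postponed treatment, with the same window in both arms. State in 9.3 or the SAP that TUDD and the mixed model use the actual completion date of each form. An interval-censored sensitivity analysis of TUDD would be a sensible addition.

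The cost is a few sentences, since the 8-weekly evaluation already exists. The small downside is that some forms may fall away from a treatment visit when a course is postponed.

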5.4 End of treatment Visit

When a patient is taken off treatment, the following assessments should be performed within 14 days after study treatment has stopped provided the last clinical and laboratory

evaluations > 7 days.

- Physical examination with weight, BSA and vital signs (heart rate, blood pressure)
- ECOG performance status
- Adverse events documentation (including Start/Stop dates, seriousness, CTC notation and grading, relationship to study drug, outcome and action taken) using CTCAE V5.0
- Concomitant medications
- 12 lead ECG

- A CBC with differential should be performed: RBC, hemoglobin, hematocrit, platelet count and WBC. WBC must include differential neutrophil, lymphocyte, monocyte, basophil and eosinophil counts
- Coagulation panel: Prothrombin time (PT) or the International Ratio of PT (PT-INR) and Partial Thromboplastin Time (PTT)
- Electrolyte panel: sodium, potassium, chloride and calcium
- Chemistry panel: albumin, lipase, phosphate, glucose, serum, creatinine, clearance calculated according CKD-EPI (appendix 7)
- Liver function test panel: Aspartate Amino-Transferase (AST), Alanine Amino-Transferase (ALT), bilirubin (total and direct), GGT, alkaline phosphatase, Lactic Dehydrogenase (LDH)
- Thyroid function test: TSH, free T3, and free T4
- Tumor markers: CEA (Carcino-Embryogenic Antigen), CA 19.9 (Carbohydrate Antigen 19-9)
- Urine analysis by urinary dipstick. If results of protein ≥ 3, then quantification
 of proteinuria on a 24-hour urine collection must be done
- A radiological tumor assessment using the RECIST criteria, version 1.1 (see Appendix 5) must be performed if the last radiological assessment > 1 months. (CT scan of the abdomen, pelvis and chest or hepatic MRI and CT scan of the pelvis and chest without injection)
- Drug accountability (pharmacy)

